5.5. Detailed description of study procedures

5.5.1. Procedures during Visit 1

Note that Visit 1 will take place at least 7 days before the first vaccination Visit (Visit 2) (see [Table 6](#) for visit intervals).

5.5.1.1. Informed consent

The signed/witnessed informed consent of the subject must be obtained before study participation. Refer to Section [5.1](#) for the requirements on how to obtain informed consent.

5.5.1.2. Check inclusion and exclusion criteria

Check all inclusion and exclusion criteria as described in Sections [4.2](#) and [4.3](#) before enrolment.

5.5.1.3. Training on the completion of SF-36 and EQ-5D questionnaires

Subjects/ subjects' caregiver(s) will be trained on completing the SF-36 and EQ-5D questionnaires at Visits 1, 2, 3, 4 and 5 (see Sections [10.6.2.3](#) and [10.6.2.4](#) for information on the SF-36 and EQ-5D questionnaires, respectively).

5.5.1.4. Distribution and completion of SF-36 and EQ-5D questionnaires

Subjects /subjects' caregiver(s) will complete the SF-36 and EQ-5D questionnaires (see Sections 10.6.2.3 and 10.6.2.4). The SF-36 and EQ-5D questionnaires will be distributed to subjects at the Pre-Vaccination Visit 1. Subjects will be asked to complete both SF-36 and EQ-5D questionnaires on Day -7 (Visit 1). Completed questionnaires will be collected at Visit 1 and subject responses transcribed into the eCRF.

5.5.1.5. Physical examination and assessment of frailty status

Perform a physical examination of the subject at Visit 1 including weight and height (body mass index [BMI] will be calculated). The physical examination can be performed per the site's medical judgment and standard of care. Collected information needs to be recorded in the eCRF. (Amended 16 November 2016)

Treatment of any abnormality observed during physical examination has to be performed according to local medical practice outside this study or by referral to an appropriate health care provider.

An assessment of frailty status defined through a Frailty Index (FI) described as accumulation of deficits, including but not limited to a series of certified tests will be done at Visit 1 and data recorded in the eCRF (see Section 10.6.2.2, *and refer to the SPM for details on the assessment of frailty status*). (Amended 16 November 2016)

5.5.1.6. Record demographic data

Record demographic data such as date of birth, gender, geographic ancestry and ethnicity*. Working status of the subject, if the subject has a caregiver (as well as the working status of the caregiver if applicable) will also be included in the subject's eCRF.

*Since differences in the safety and efficacy of certain medical products have been observed in racially and ethnically distinct subgroups of the US population, ethnicity will be collected.

5.5.1.7. Medical history

Obtain the subject's medical history by interview and/or review of the subject's medical records and record any pre-existing conditions or signs and/or symptoms present in a subject prior to the first visit in the eCRF. Medications taken by the subject must also be recorded.

5.5.1.8. Distribution, training, completion and collection of pre-vaccination diary card

A pre-vaccination diary card will be dispensed to each subject prior to the first study vaccination and subjects/ subjects' caregiver will be informed how to complete this card by the site staff. This pre- vaccination diary card will only query general symptoms and

should be completed by the subject /subjects' caregiver(s) and collected by the site staff at Visit 1.

5.5.1.9. Review and transcribe pre-vaccination diary cards

The investigator/study staff will ensure that subject has completed the Visit 1 pre-vaccination diary card. The investigator or designee will transcribe the information that the subject documented on the diary card into the eCRF.

5.5.2. Procedures during Visit 2

Note that the first vaccination at Visit 2 will take place at least 7 days after the first visit (Visit 1) (see [Table 6](#) for visit intervals).

5.5.2.1. Re-check inclusion and exclusion criteria

Inclusion and exclusion criteria are re-checked at Visit 2 for any changes compared to Visit 1. In case the subject is no longer eligible at Visit 2, the subject will be withdrawn from the study and the reason for this will be recorded in the eCRF. If the investigator or delegate determines that the subject's health on the day of administration temporarily precludes vaccine administration, the visit will be rescheduled within the allowed interval for this visit (refer to [Table 6](#) for visit intervals).

5.5.2.2. Distribution, completion and collection of second pre-vaccination diary card

A second pre-vaccination diary card will be dispensed to each subject at Visit 2. The card will only query general symptoms and should be completed by the subject /subjects' caregiver(s) and collected by the site staff prior to the first study vaccination.

5.5.2.3. Review and transcribe pre-vaccination diary cards

The investigator/study staff will ensure that subject has completed the (Visit 2) pre-vaccination diary cards prior to Vaccination 1. The investigator or designee will transcribe the information that the subject documented on the diary card prior to the visit into the eCRF.

5.5.2.4. Distribution and completion of SF-36 and EQ-5D questionnaires at Visit 2

The SF-36 and EQ-5D questionnaires will be distributed to subjects again at Visit 2. Subjects will be asked to complete the entire SF-36 and EQ-5D questionnaires on site just before vaccination at Visit 2. Completed questionnaires will then be collected and subject responses will be transcribed into the e-CRF. The same procedure for questionnaires will be followed at Visit 4 (see Section [5.5.2.11](#)).

5.5.2.5. Check contraindications

Contraindications must be checked at the beginning of each vaccination visit. Refer to Section [6.4](#) for more details.

5.5.2.6. Pregnancy test

Female subjects of childbearing potential are to have a urine pregnancy test* prior to any study vaccine administration. The study vaccine may only be administered if the pregnancy test is negative. Note: The urine pregnancy test must be performed even if the subject is menstruating at the time of the study visit.

*A urine pregnancy test is sufficient. A serum pregnancy test, instead of a urine pregnancy test, should only be considered if required by local or ethics committee regulations.

5.5.2.7. Assess pre-vaccination body temperature

The body temperature of all subjects needs to be measured prior to any study vaccine administration. Pre-vaccination temperatures should always be recorded orally. In rare situations when there is no other alternative, the temperature may be recorded by other route. If the temperature is taken by another route (axillary, rectal or tympanic), the route should be documented and justified. If the subject has a fever (fever is defined as temperature $\geq 37.5^{\circ}\text{C}/99.5^{\circ}\text{F}$ by oral route, axillary or tympanic setting, or $\geq 38.0^{\circ}\text{C}/100.4^{\circ}\text{F}$ on rectal setting) on the day of vaccination, the vaccination visit will be rescheduled within the allowed interval for this visit (see [Table 6](#) for visit intervals).

5.5.2.8. Study vaccine administration

- After completing all prerequisite procedures prior to vaccination, one dose(s) of HZ/su study vaccine will be administered IM in the deltoid of the non-dominant arm (refer to Section [6.3](#) for detailed description of the vaccine administration procedure). If the investigator or delegate determines that the subject's health on the day of administration temporarily precludes vaccine administration, the visit will be rescheduled within the allowed interval for this visit (refer to [Table 6](#) for visit intervals). In that case, all activities that need to be performed on the day of vaccination (e.g., pregnancy test, questionnaires completion, ...) will also have to be postponed until vaccination day.
- The subjects will be observed closely for at least 30 minutes following the administration of the vaccine(s), with appropriate medical treatment readily available in case of anaphylaxis.
- Any subjects with an event of HZ between Visit 1 (Day -7) and any dose of HZ/su vaccine should not receive the upcoming dose(s) of the HZ/su vaccine.

5.5.2.9. Check and record concomitant medication/vaccination

Concomitant medication/vaccination must be checked and recorded in the eCRF as described in Section [6.5](#).

5.5.2.10. Recording of AEs, SAEs, pregnancies and pIMDs

- Refer to Section [8.3](#) for procedures for the investigator to record AEs, SAEs, pregnancies and pIMDs. Refer to Section [8.4](#) for guidelines and how to report SAE, pregnancy and pIMD reports to GSK Biologicals.
- The subjects/subjects' caregiver(s) will be instructed to contact the investigator immediately should the subjects manifest any signs or symptoms they perceive as serious.
- At each vaccination visit, diary cards will be provided to the subject/subject's caregiver(s) see Section [5.3.1.1](#)). The subject/subject's caregiver(s) will record body (oral route preferred) temperature and any solicited local/general AEs (i.e., on the day of vaccination and during the next 6 days) or any unsolicited AEs (i.e., on the day of vaccination and during the next 29 days occurring after vaccination). If the temperature is taken by another route (axillary, rectal or tympanic), the route should be documented with an explanation for why it was different from the oral route. The subject/subject's caregiver(s) will be instructed to return the completed diary cards.
- The subject/subject's caregiver(s) will be instructed to return the completed diary card to the investigator at the next study visit. The post-vaccination 2 diary cards for daily recording of unsolicited AEs and concomitant medication/vaccination (Days 0-29) by subjects will be returned by mail.
- Collection and verification of completed diary cards will occur during discussion with the subject/ subject's caregiver(s) at the visit following each vaccination visit (except for the post-vaccination 2 diary cards for daily recording of unsolicited AEs and concomitant medication/vaccination (Days 0-29) which will be returned by mail and discussed during the Month 3 phone contact).
- Any unreturned diary cards will be sought from the subject/subject's caregiver(s) through telephone call(s) or any other convenient procedure. The investigator and/or delegate will transcribe the collected information into the eCRF.

5.5.2.11. Distribution and completion of SF-36 and EQ-5D questionnaires post-vaccination

The SF-36 PF component of the SF-36 questionnaire (only questions 3a through 3j, see [Table 15](#)) and EQ-5D daily questionnaires will be distributed to the subjects to take home following both vaccinations at Visit 2 and Visit 4. These questionnaires will need to be completed on a daily basis (Days 1 to 6) and must be returned at the next visits (Visit 3 and Visit 5). Additionally, during Visits 3 and 5, subjects will be asked to once again fill in the entire SF-36 and EQ-5D questionnaires on site. Completed questionnaires, collected at Visits 3 and Visit 5, will be transcribed into the eCRF (see Sections [10.6.2.3](#) and [10.6.2.4](#)).

5.5.3. Study conclusion

The investigator will:

- Review data collected to ensure accuracy and completeness,
- Complete the Study Conclusion screen in the eCRF.

6. STUDY VACCINE AND ADMINISTRATION

6.1. Description of study vaccine

The candidate vaccine to be used has been developed and manufactured by GSK Biologicals.

The Quality Control Standards and Requirements for the candidate vaccine are described in separate Quality Assurance documents (e.g., release protocols, certificate of analysis) and the required approvals have been obtained.

The vaccine is labelled and packed according to applicable regulatory requirements.

The characteristics of the study vaccine are detailed in [Table 7](#).

Table 7 Study vaccine

Treatment name	Vaccine name	Formulation	Presentation	Volume to be administered	Number of doses
HZ/su	VZV gE	gE=50µg	Lyophilized pellet in a vial	0.5 mL	2
	AS01B	MPL=50µg; QS21=50µg; Liposomes	Liquid in a mono-dose vial		

HZ/su = Herpes Zoster subunit vaccine; VZV = Varicella Zoster Virus; gE = recombinant purified envelope glycoprotein E; µg = microgram; mL = milliliter; AS01_B = Adjuvant System AS01_B; MPL = 3-O-desacyl-4'-monophosphoryl lipid A; QS21 = *Quillaja saponaria* Molina, fraction 21 (purified saponin extract from the South American tree).

6.2. Storage and handling of study vaccine

The study vaccine must be stored at the respective label storage temperature conditions in a safe and locked place. Access to the storage space should be limited to authorized study personnel. The storage conditions will be assessed during pre-study activities under the responsibility of the sponsor study contact. The storage temperature should be continuously monitored with calibrated (if not validated) temperature monitoring device(s) and recorded. Refer to the Module on Clinical Trial Supplies in the SPM for more details on storage of the study vaccine.

Temperature excursions must be reported in degree Celsius.

Any temperature excursion outside the range of 0.0 to +8.0°C (for +2 to +8°C/+36 to +46°F label storage condition) impacting investigational medicinal products (IMPs) must

be reported in the appropriate (electronic) temperature excursion decision form ([e]TDF). The impacted IMPs must not be used and must be stored in quarantine at label temperature conditions until usage approval has been obtained from the sponsor.

In case of temperature excursion below +2.0°C down to 0.0°C impacting IMP(s) there is no need to report in (e)TDF, but adequate actions must be taken to restore the +2 to +8°C/+36 to +46°F label storage temperature conditions. The impacted IMP(s) may still be administered, but the site should avoid re-occurrence of such temperature excursion. Refer to the Module on Clinical Trial Supplies in the SPM for more details on actions to take.

Refer to the Module on Clinical Trial Supplies in the SPM for details and instructions on the temperature excursion reporting and usage decision process, packaging and accountability of the study vaccine.

6.3. Dosage and administration of study vaccine

After removal of the vaccine components from the temperature monitored refrigerator, the vaccine should be reconstituted and administered within 6 hours, and should be kept at room temperature (between 2°C/36°F and 30°C/86°F).

Vaccine will be administered as indicated in [Table 8](#).

Table 8 Dosage and administration

Type of contact and timepoint	Study group	Treatment name	Volume to be administered	Route ¹	Site ²	Side ³
Visit 2 (Month 0)						
Visit 4 (Month 2)	HZ/su	HZ/su	0.5 mL	IM	D	N-D

¹ Intramuscular (IM)

² Deltoid (D)

³ Non-dominant (N-D)

mL = millilitre; HZ/su = Herpes Zoster subunit vaccine.

The reconstituted vaccine (0.5 mL) should be administered by IM injection into the deltoid (D) muscle of the non-dominant (N-D) arm using a standard aseptic technique. In rare situations when there is no alternative, the injection may be given in the dominant arm.

6.4. Contraindications to subsequent vaccination

The following events constitute absolute contraindications to further administration of HZ/su vaccine. If any of these events occur during the study, the subject must not receive additional doses of vaccine but may continue other study procedures at the discretion of the investigator (see [Section 8.5](#)).

- Anaphylaxis following the administration of vaccine.
- Pregnancy (see [Section 8.2.1](#)).

- Any condition that in the judgment of the investigator would make intramuscular injection unsafe.
- If the subject experiences an SAE judged to be vaccine-related by the investigator/ delegate.
- If the subject experiences an event of HZ before administration of the first dose of the vaccine or between the first and the second dose of vaccine.
- Any confirmed or suspected immunosuppressive or immunodeficient condition, including HIV infection.
- Occurrence of a new pIMD or the exacerbation of an existing pIMD that, in the opinion of the investigator, expose the subject to unacceptable risk from subsequent vaccination. In such cases, the investigator should use his/her clinical judgment prior to administering the next dose of the vaccine. Refer to Section 8.1.5.1 for the definition of pIMDs.

The following events constitute contraindications to administration of HZ/su vaccine at that point in time; if any of these events occur at the time scheduled for vaccination, the subject may be vaccinated at a later date, within the time window specified in the protocol (see Section 5.4), or the subject may be withdrawn at the discretion of the investigator (see Section 8.5).

- Acute disease and/or fever at the time of vaccination.
 - Fever is defined as temperature $\geq 37.5^{\circ}\text{C}/99.5^{\circ}\text{F}$ for oral, axillary or tympanic setting, or $\geq 38.0^{\circ}\text{C}/100.4^{\circ}\text{F}$ for rectal route. The preferred route for recording temperature in this study will be oral.
 - Subjects with a minor illness (such as mild diarrhea, mild upper respiratory infection) without fever can be administered all vaccines/products.

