8.2. Events or outcomes not qualifying as adverse events or serious adverse events

8.2.1. Pregnancy

Female subjects who are pregnant or lactating at the time of vaccination must not receive additional doses of study vaccine but may continue other study procedures at the discretion of the investigator.

While pregnancy itself is not considered an AE or SAE, any adverse pregnancy outcome or complication or elective termination of a pregnancy for medical reasons will be recorded and reported as an AE or a SAE.

Note: The pregnancy itself should always be recorded on electronic pregnancy report.

The following should always be considered as SAE and will be reported as described in Sections 8.4.1 and 8.4.3:

- Spontaneous pregnancy loss, including:
 - spontaneous abortion, (spontaneous pregnancy loss before/at 22 weeks of gestation)
 - ectopic and molar pregnancy
 - stillbirth (intrauterine death of foetus after 22 weeks of gestation).
- Note: the 22 weeks cut-off in gestational age is based on WHO-ICD 10 noted in the EMA Guideline on pregnancy exposure [EMA, 2006]. It is recognized that national regulations might be different.
- Any early neonatal death (i.e., death of a live born infant occurring within the first 7 days of life).

- Any congenital anomaly or birth defect (as per [CDC MACDP 2007] guidelines) identified in the offspring of a study subject (either during pregnancy, at birth or later) regardless of whether the foetus is delivered dead or alive. This includes anomalies identified by prenatal ultrasound, amniocentesis or examination of the products of conception after elective or spontaneous abortion.

Furthermore, any SAE occurring as a result of a post-study pregnancy AND considered by the investigator to be reasonably related to the investigational vaccine will be reported to GSK Biologicals as described in Section 8.4.3. While the investigator is not obligated to actively seek this information from former study participants, he/she may learn of a pregnancy through spontaneous reporting.

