8.3. Detecting and recording adverse events, serious adverse events and pregnancies

8.3.1. Time period for detecting and recording adverse events, serious adverse events and pregnancies

All AEs starting 30 days following administration of each dose of study vaccine must be recorded into the appropriate section of the eCRF, irrespective of intensity or whether or not they are considered vaccination-related.

The time period for collecting and recording SAEs will begin at the first receipt of study vaccine and will end approximately 12 months following administration of the last dose of study vaccine for each subject. See Section 8.4 for instructions on reporting of SAEs.

All AEs/SAEs leading to withdrawal from the study will be collected and recorded from the time of the first receipt of study vaccine.

In addition to the above-mentioned reporting requirements and in order to fulfil international reporting obligations, SAEs that are related to study participation (i.e., protocol-mandated procedures, invasive tests, a change from existing therapy) or are related to a concurrent GSK medication/vaccine will be collected and recorded from the time the subject consents to participate in the study until she/he is discharged from the study.

The time period for collecting and recording pregnancies will begin at the first receipt of study vaccine and will end 12 months following administration of the last dose of study vaccine. See Section 8.4 for instructions on reporting of pregnancies.

The time period for collecting and recording of pIMDs will begin at the first receipt of study vaccine and will end 12 months following administration of the last dose of study vaccine. See Section 8.4 for instructions on reporting of pIMDs.

An overview of the protocol-required reporting periods for AEs, SAEs, and pregnancies is given in [Table 12](#).

Table 12 Reporting periods for collecting safety information

Timepoint	Visit 1 Day -7	Visit 2 Month 0	Visit 3 Day 7	Month 1	Visit 4 Month 2	Visit 5 Day 67	Contact Month 3		Contact Month 8		Contact Month 14
Timing of reporting / Study activity	Day -7 Pre-Vacc.	Day 0 Dose 1	Day 6 post-Dose 1	Day 29 post-Dose 1	Day 60 Dose 2	Day 6 post-Dose 2	Day 29 post-Dose 2		Safety Follow-Up		Study Conclusion
Solicited general AEs (see Sections 5.3.1.1 and 5.5.1.8) (Amended 16 November 2016)											
Solicited local AEs											
Unsolicited AEs ^a											
AEs/SAEs leading to withdrawal from the study											
SAEs											

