8.5.1.2. Follow-up after the subject is discharged from the study

The investigator will follow subjects:

- with SAEs, pIMDs (serious or non-serious), or subjects withdrawn from the study as a result of an AE, until the event has resolved, subsided, stabilised, disappeared, or until the event is otherwise explained, or the subject is lost to follow-up.

If the investigator receives additional relevant information on a previously reported SAE, he/she will provide this information to GSK Biologicals using a paper/ electronic Expedited Adverse Events Report and/or pregnancy report as applicable.

GSK Biologicals may request that the investigator performs or arranges the conduct of additional clinical examinations/tests and/or evaluations to elucidate as fully as possible the nature and/or causality of the AE or SAE. The investigator is obliged to assist. If a subject dies during participation in the study or during a recognised follow-up period, GSK Biologicals will be provided with any available post-mortem findings, including histopathology.

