9.2.1. Subject withdrawal from the study

From an analysis perspective, a 'withdrawal' from the study refers to any subject who was not available for the concluding contact foreseen in the protocol.

All data collected until the date of withdrawal/last contact of the subject will be used for the analysis.

A subject is considered a 'withdrawal' from the study when no study procedure has occurred, no follow-up has been performed and no further information has been collected for this subject from the date of withdrawal/last contact.

Investigators will make an attempt to contact those subjects who do not return for scheduled visits or follow-up.

Information relative to the withdrawal will be documented in the eCRF. The investigator will document whether the decision to withdraw a subject from the study was made by the subject himself/herself, by the subject's caregiver(s), or by the investigator, as well as which of the following possible reasons was responsible for withdrawal:

- Serious adverse event.
- Non-serious adverse event.
- Protocol violation (specify).
- Consent withdrawal, not due to an adverse event*.
- Moved from the study area.
- Lost to follow-up.
- Other (specify).

*In case a subject is withdrawn from the study because he/she/the subject's caregiver(s) has withdrawn consent, the investigator will document the reason for withdrawal of consent, if specified by the subject/subject's caregiver(s), in the eCRF.

Subjects who are withdrawn from the study because of SAEs/AEs must be clearly distinguished from subjects who are withdrawn for other reasons. Investigators will follow subjects who are withdrawn from the study as result of a SAE/AE until resolution of the event (see Section 8.5.1.2).

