9.2.2. Subject withdrawal from investigational vaccine

A 'withdrawal' from the investigational vaccine refers to any subject who does not receive the complete treatment, i.e., when no further planned dose is administered from the date of withdrawal. A subject withdrawn from the investigational vaccine may not necessarily be withdrawn from the study as further study procedures or follow-up may be performed (safety or immunogenicity) if planned in the study protocol.

Information relative to premature discontinuation of the investigational vaccine will be documented on the Vaccine Administration page/screen of the eCRF. The investigator will document whether the decision to discontinue further vaccination/treatment was made by the subject himself/herself, by the subject's caregiver(s), or by the investigator, as well as which of the following possible reasons was responsible for withdrawal:

- Serious adverse event.
- Non-serious adverse event.
- Other (specify).

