### 7.2.2. Reactogenicity and safety

For a given subject and a given measurement, missing or non-evaluable measurements will not be imputed. The missing endpoint and censoring are supposed to occur independently, and the pattern of the missing value(s) being either Missing Completely At Random (MCAR) or Missing At Random (MAR) only.

For the analysis of solicited symptoms, missing or non-evaluable measurements will not be replaced. Therefore the analysis of the solicited symptoms based on the TVC will include only subjects/doses with documented safety data (i.e., symptom screen/sheet completed).

For the analysis of unsolicited symptoms/SAEs/pIMDs/concomitant medication, all vaccinated subjects will be considered and subjects who did not report an event will be considered as subjects without an event.

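### Once a vaccinated subject misses dose 2, Section 6.4 makes further follow-up optional, and the SAP counts later unobserved AEs, SAEs and pIMDs as no event

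*Protocol*

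**What the plan says.** Protocol Section 6.4 has two paragraphs that matter here.

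- **Barred subjects.** The events that rule out a further dose include anaphylaxis, a vaccine-related SAE, HZ, pregnancy, immunodeficiency, and a new or worsened pIMD judged too risky. After any of these, "the subject must not receive additional doses of vaccine but may continue other study procedures at the discretion of the investigator".
- **Deferred subjects.** With acute disease or fever at a vaccination visit, the subject may be vaccinated later within the window, "or the subject may be withdrawn at the discretion of the investigator".

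Section 8.2.1 gives the same latitude for a pregnant or lactating subject, who "may continue other study procedures at the discretion of the investigator".

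Section 8.3.1 sets the collection period without such latitude. SAE collection starts at the first dose and "will end approximately 12 months following administration of the last dose of study vaccine for each subject". pIMDs and pregnancies have the same 12 months. Section 10.2 carries the SAE and pIMD endpoints to study end.

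Section 9.2.2 separates stopping vaccine from leaving the study: "A subject withdrawn from the investigational vaccine may not necessarily be withdrawn from the study". Section 9.2.1 says "All data collected until the date of withdrawal/last contact of the subject will be used for the analysis". After discharge, Section 8.5.1.2 requires follow-up of subjects with SAEs or pIMDs and of "subjects withdrawn from the study as a result of an AE, until the event has resolved". Section 8.3.2 does not oblige investigators to look actively for events in former participants.

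For unsolicited symptoms, SAEs, pIMDs and concomitant medication, SAP 7.2.2 takes all vaccinated subjects and states that "subjects who did not report an event will be considered as subjects without an event". SAP Table 3 gives the same denominator for unsolicited symptoms and SAEs.

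**The concern.** Three rules meet in one small group: follow-up that the investigator may end, a collection period fixed for each subject, and an analysis that reads silence as absence. They cannot all hold and still give a sound percentage. If a one-dose subject's procedures stop at Month 2, any later unsolicited AE, SAE or pIMD goes unseen, yet the subject stays in the denominator as free of it.

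The loss need not be random. Some of the listed reasons for missing dose 2 are safety events after dose 1. Section 1.3.1 names close pIMD monitoring as the mitigation for the theoretical autoimmune risk, and Section 6.4 makes procedures optional for a subject whose dose 1 pIMD barred dose 2. The study has one arm and no control group, so a few unobserved subjects scored as event-free would not show in the tables.

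**Working it through.** **1. Does another section close the gap?**

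- Section 8.5.1.2 follows events already known. It does not look for new ones.
- Section 8.3.2 releases the investigator from actively seeking events in former participants.
- Section 9.2.2 permits follow-up after vaccine withdrawal but does not require it.
- Section 8.5.2 requires a pregnancy to be followed to its outcome. That covers the pregnancy, not unrelated later SAEs or pIMDs.

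The gap for new events therefore remains.

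**2. Which data are affected?**

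- The triggering SAE or pIMD is reported (Section 8.4.1), followed, and kept in the analysis (Section 9.2.1). The subject is already positive for it.
- The no-event rule covers unsolicited AEs, SAEs, pIMDs and medication. Missing solicited symptoms are not replaced (SAP 7.2.2), and no QoL rule sets missing data to no loss (SAP 7.1.3.4, 7.2.3).
- Deferral at Visit 2 precedes any dose, so subjects withdrawn then are not in the vaccinated cohort. Only Visit 4 matters.

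**3. Size of the safety under-count.** The documents give none of these inputs, so all are assumptions: w, the share of vaccinated subjects who leave at Month 2 (1-3%); RR, their event risk relative to the others (1-3); p, the 14-month SAE risk (5%); and a constant hazard, so that 12/14 of the risk falls after Month 2.

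- Missed subjects = 400 × w × p × RR × 12/14.
- Total with an event = 400 × p × [(1 − w) + w × RR].
- Relative under-count = w × RR × (12/14) / [(1 − w) + w × RR]. This does not depend on p.

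| w | RR | Missed of 400 | Total with event | Under-count |
|---|---|---|---|---|
| 1% | 1 | 0.17 | 20.0 | 0.9% |
| 1% | 3 | 0.51 | 20.4 | 2.5% |
| 3% | 1 | 0.51 | 20.0 | 2.6% |
| 3% | 3 | 1.54 | 21.2 | 7.3% |

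In the last row the reported percentage is (21.2 − 1.54)/400 = 4.91% against a true 5.3%. With p = 2% the missed number runs from 0.07 to 0.62. As an outer case, w = 10% with RR = 3 gives 21.4%, or 5.1 subjects at p = 5%.

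The 12/14 factor counts events to study end, as Section 10.2 does. Under Section 8.3.1 a one-dose subject's period closes near Month 12. The factor 10/14 then gives 400 × 0.01 × 0.05 × 1 × 10/14 = 0.14 to 400 × 0.03 × 0.05 × 3 × 10/14 = 1.29 missed subjects.

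**4. Primary endpoint.** The plan's precision reproduces: 1.96 × 21.2/√360 = 2.19 against the stated 2.2 (95% two-sided confidence assumed), and 360/0.9 = 400. The dose 1 PF mean over days 1-7 can be touched only if procedures stop before Visit 3. If 1-2 of 400 subjects with an assumed 40-point drop lost all their forms, the mean would move by 0.0025 × 40 = 0.1 to 0.005 × 40 = 0.2 points. The direction is not fixed. Losing all forms would understate the PF loss. Keeping only the early days could overstate it, because Section 1.2.1 describes symptoms of about 2-3 days on average. For QALY, SAP 7.1.3.4 computes the AUC from however many assessments exist, so a truncated curve gives a smaller area and a larger loss.

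**The case against.** The strongest reply is that the protocol already points towards retention. Section 3 forbids waivers and calls the scheduled procedures required. Section 9.2.2 separates vaccine withdrawal from study withdrawal. Section 9.2.1 asks sites to try to contact subjects who do not return, and Section 8.3.3.4 asks about medical attention to Month 14. Section 6.4 does not say that a deferred subject is withdrawn from the study as a whole. The analysis is descriptive with no success criterion (Section 10.7), the numbers are small, and the table shells are in a separate annex that may already hold a follow-up count.

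Much of this stands, and it limits the point to a clarification. It does not remove it: a general requirement and an explicit local discretion still pull in different directions, and a site with a barred subject will read Section 6.4.

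A reader might go further and infer that the worst reactors drop out and are scored as event-free, so that the primary PF loss is understated. The documents do not support that. Grade 3 reactogenicity is not a listed contraindication, and several listed items are not reactions at all. Deferral for fever or acute disease arises 49-83 days after dose 1 (Table 6), well after the solicited period. A barred subject has no dose 2 QoL to lose, whatever the investigator decides.

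**Conclusion.** The point holds for later safety events. Section 6.4 (both paragraphs) and Section 8.2.1 permit follow-up to end in vaccinated subjects who miss dose 2. Section 8.3.1 assumes that it continues, and SAP 7.2.2 scores the unobserved remainder as no event in a full denominator.

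The size is small: 0.9-7.3% of subjects with an SAE, about 0.2-1.5 of 400, if 1-3% leave at Month 2 with relative risk 1-3 and a 14-month risk of 5%. These inputs are illustrative. The upper end leans towards a ceiling for the SAE table, since a subject barred for a related SAE already counts there and a later SAE would change only a different preferred-term row. The effect on the primary endpoint is negligible and of unestablished direction. It is worth correcting because the loss can be tied to a dose 1 safety event and the correction is cheap.

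**What to change.** Reconcile Sections 6.4 (both paragraphs), 8.2.1 and 9.2.2 with Section 8.3.1, leaving every dosing decision unchanged.

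1. State that for a subject with at least one dose, not receiving dose 2 ends dosing only. Outstanding post-dose 1 questionnaires and diary cards, and SAE, pIMD and pregnancy collection to 12 months after the last dose received, remain required unless consent is withdrawn.
2. State how the Month 3, Month 8 and Month 14 contacts are timed for a one-dose subject. Table 6 counts all three from Visit 4, so 12 months after a single dose falls near Month 12, where no contact is scheduled.
3. In the SAP, show the number of vaccinated subjects not followed to the end of the collection period beside the SAE and pIMD percentages, if the table shells do not already do so.

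The cost is a few sentences of protocol text, a few extra contacts and one table count. The sample size does not change.
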